**Patients with head and neck cancer treated by radiotherapy: The
impact of fixed dentures on wellbeing and oral health related
quality of life.**

Introduction

Head and neck neoplasms are defined as tumours in the upper aerodigestive tract. The tumours origin from different tissues such as the carcinomas arising from the epithelium, and sarcomas from bone, cartilage, fat, muscle, vascular, or hematopoietic tissues. Lymphomas are tumours in the lymphoid system, and melanomas arise from melanocytes, melanin-producing cells in the skin. The sites affected by the tumour are the lips, oral cavity, pharynx, larynx, and cervical oesophagus, the nose and paranasal sinuses, salivary glands, thyroid gland and parathyroid glands, and melanoma and non-melanoma skin cancers of the head and neck (1). Head and neck cancer is the fifth most common cancer worldwide with an estimated global incidence of more than 500 000 cases per year (2). Tobacco use and alcohol consumption are the most important risk factors for these cancers, while a subgroup is caused by viral infections. Patients with early-stage disease are treated by surgery or radiotherapy, whereas patients in advanced stages receive a combination of these modalities or concurrent chemotherapy and localized radiation. The five-year survival rate after treatment is around 40-50 % (3).

Patients with head and neck cancer treated by radiotherapy suffer from acute and long-term oral side effects. Oral mucositis, pain, dysphagia, and superficial opportunistic infections are common acute side effects that in most cases cease within one month after radiotherapy has been completed. However, long-term side effects like hyposalivation, impaired taste, and trismus may be life long conditions. Moreover, altered microbiological flora of the mouth, attenuated tooth enamel, and hyposalivation are risk factors for dental caries (4-6). Other hard tissue damages caused by radiotherapy are periodontitis, and more severely osteoradionecrosis of the jaws (7). The latter condition

is caused by poor vasculated bone. Teeth with poor prognosis should be extracted before radiotherapy begins, leading to impaired occlusion including dysfunctional aesthetics and mastication. The Swedish National Board of Health and Welfare regulations compensate extracted teeth with removable dental prostheses/dentures (8). However, using removable dentures in patients with hyposalivation after radiotherapy is complicated. Removable dentures retain poorly, or chafe the oral mucosa leading to pain in function. Also, there may be problems maintaining good dental and denture hygiene leading to dental caries and periodontitis.

To date, the impact of dental occlusion on these patients' quality of life is sparsely investigated. In one study, implant-retained mandibular overdentures in patients treated for oral cancers were followed over five years (9). Overall, the survivors' oral function and patient satisfaction were high and did not change. Impaired global health and quality of life were associated with concurrent comorbidity. Malnutrition, associated with increased morbidity and mortality, in patients treated for oral/oropharyngeal cancers was shown to impair physical functioning and hence quality of life (10). In this study dental status was poorly described, although dry mouth, pain in the mouth, and problems with social contact correlated well to malnutrition and fatigue. Speech after surgery was more impaired in patients with oral cancers than with oropharyngeal cancers because of loss of anatomically important articulatory structures leading to decreased quality of life. However, there are no prospective studies supporting better speech outcome after radiotherapy alone compared with surgery (11).

Therefore, the aim of this project was to evaluate the effect and cost effectiveness of prosthodontic rehabilitation on oral health related quality of life, general wellbeing, and nutrition in patients treated by radiotherapy, with or without combination of

chemotherapy or surgery against head and neck cancer.

Methods

Design and setting

In this project, an interventional case-control study will be undertaken in four middle sized counties in the south of Sweden. Based on the case control sample also a methodological study will be realized in order to test the measurements' validity and reliability, but also a descriptive qualitative content analysis study will be accomplished. All these measurements – called triangulation – are done in order to strengthen the case-control study as a power calculation is not relevant to do due to the restricted eligible/consecutive sample as well as the restricted time schedule. Finally, based on all available data, a cost-effectiveness analysis will be undertaken with the use of a decision analytic model.

Intervention

Standard treatment

In order to replace extracted teeth after radiotherapy, the standard treatment is temporary removable dental prostheses/dentures (partial or complete). Depending on the teeth remaining, those may be completely tooth or tissue supported, or tissue and tooth supported. Temporary partial dentures are completely out of acrylic. Efforts are made to design a self-cleansing partial denture that preserves the remaining teeth and oral structures. The chewing forces are distributed evenly over the entire remaining teeth and soft tissues. Oral health related quality of life in healthy patients wearing removable dentures has previously been shown (12).

Fixed dentures

The special treatment is to within a year after completed radiotherapy replace removable dentures with tooth- or implant-supported dentures. The special treatment will begin six months after completed radiotherapy, or later depending on the severity of the side effects. Tooth- and implant-supported dentures are accepted modalities in patients with total or partial edentulous (13, 14). Patients with head and neck cancers usually follow the dental implant protocol valid for healthy individuals (15, 16). However, the fixture installation will be within a year after finished radiotherapy, when the jaws are still well supplied.

Participants

The study will take place in four middle sized counties in the south of Sweden. The intervention will include 30 patients with head and neck cancer recruited from a Department of Maxillofacial and Oral Surgery (the City of Jönköping, Jönköping County Council), and from the Department of Orofacial Medicine (the City of Stockholm, Stockholm County Council). Another 30 patients with the same disease will be matched controls recruited from another Department of Maxillofacial and Oral Surgery (the City of Linköping, County Council of Östergötland) and from five Departments of Orofacial Medicine (the Cities of Kalmar, Oskarshamn, and Västervik, Kalmar County Council; the Cities of Ljungby, and Växjö, Kronoberg County Council). If possible but not necessary, those controls may be prosthodontically rehabilitated with temporary removable dentures. The retest described in data collection study one will include ten patients diagnosed with head and neck tumor. All patients in the retest will be residents in the County of Jönköping.

The inclusion criteria are patients with head and neck tumours considered to receive radiotherapy, with or without combination of chemotherapy or surgery, good oncological prognosis at baseline ($\leq T2$). After referral from an ENT-specialist, those patients being diagnosed with dental infections and therapy planned for dental extraction(s) will be included.

The following general exclusion criteria will be applied: any communication problems; any comorbidity with poor prognosis; poor oncological prognosis (TNM-classification $>T2$) at baseline; imminent risk of recurrence; any technical, biological, or any other reasonable obstacle of treating patients with fixed dentures; and finally patients in the matched control group financing fixed oral prosthesis themselves.

Background data like sex, age, diagnosis, TNM-classification, hyposalivation, vertical jaw mobility, dysphagia, number and sites of extracted teeth, and weight will be investigated.

Study one – quantitative approach

Instruments

SF-36v2

SF-36v2 is a well established psychometric instrument with 36 items measuring eight domains of health-related quality of life: Physical function, physical role function, bodily pain, general health, vitality, social function, emotional role function, mental health. The two comprehensive indices – physical health and mental health - can be estimated for. The instrument is translated and validated into Swedish (17-19).

EQ-5D

EQ-5D is an instrument containing five items measuring mobility, self-care, pain, role function, and anxiety/depression. There is also one item considering change of health condition and a VAS scale for general health. This instrument is also translated and validated into Swedish (20-22).

Oral health impact profile (OHIP)

OHIP-14 is an instrument consisting of 14 items (23). It was designed to provide a comprehensive measure of the dysfunction, discomfort and disability attributed to oral conditions. Validated Swedish versions of the OHIP-14 are available (24, 25).

General oral health assessment index (GOHAI)

GOHAI is a 12-item instrument originally developed for use with older adult populations, although more recently it has been used with populations of younger adults. It measures oral functional problems and also assesses the psychosocial impacts associated with oral disease (26). A Swedish version has been validated (27).

The Jaw Functional Limitation Scale (JFLS-8)

The JFLS-8 was developed for assessing limitations in mastication, jaw mobility, and verbal and emotional expression. It is recommended for clinical and research use in patient groups with varying functional limitations of the jaw. The instrument has been tested for reliability and validity (28, 29).

The Orofacial Aesthetic Scale (OAS)

The OAS consists of seven separate aesthetic aspects of the face, teeth, lips, and mouth — devoid of psychosocial aspects. These seven items create the OAS summary score. There is also an eight item, global assessment of overall impact. A Swedish version has

been validated (28, 30, 31).

Data collection

The written consent among with the instruments will be distributed to the patients at the clinic at baseline (before any treatment), appendix 4. The completed documents will be returned to a research coordinator/dental assistant at the Department of

Maxillofacial and Oral Surgery (the City of Jönköping, Jönköping County Council).

Measurements and administration of the instruments after baseline follow the study protocol, appendix 13. The study protocol after completed radiotherapy states measurements at approximately 6 and 12 months respectively, or in severe cases after the prostheses have been used for one month. Those patients who receive the instruments by mail, will be requested to immediately respond to the instruments and return them to the research coordinator in attached envelopes (prepaid postage). A reminder is sent to the patient after one and two weeks if not responding. If necessary after another week, the patient will be contacted by telephone by the research coordinator. The patients weight will be recorded at the clinic, or self-reported by mail.

Data analysis

Parametric as well as non-parametric methods will be used in the statistical inference testing. Thus, for comparison between two groups the Student t-test and the Mann-Whitney U-test and between three groups or more Two-Way Analysis of Variance the Kruskal-Wallis One-Way Anova will be applied. For comparison of proportions between groups the Chi-square-test including standardized residual are to be used. For analysing changes over time the paired t-test or the Wilcoxon Signed Rank Test (for continuous variables) or the McNemar Test (for dichotomised variables) will be applied. For estimating relation between two continuous variables the Pearson test or Spearman

Rank Order Correlation will be used. For prediction, multiple and logistic regression are to be used and in order to adjust for confounding variables such as age logistic regressions also are to be used. The pre-chosen level of significance will be $p<0.05$ in all analyses.

Study two – qualitative approach

Interviews

A dental assistant experienced in methodological or subject experiences will interview the patients during approximately one hour twice. The dialogue will start with questions on general wellbeing, and then approaching oral health related quality of life. All the interviews will start with the question “How do you feel with regard to your health?”, followed by “Can you tell me more?”. Eventually the dental assistant asks, “How do you feel with regard to your mouth?” The interview will result in a detailed and exhaustive story from different point of views. All interviews will be recorded on minidiscs.

Data collection

The first interview will take place approximately six months after completed radiotherapy, and the second one after approximately 12 months.

Data analysis

Qualitative content analysis described by Hsieh and Shannon (32) will be used in analysing the interviews. Each interview will be listened to in order to gain a general understanding of the content. Any content relevant to the aim will be analyzed. The text will be condensed and labelled using codes, being careful not to change the core of the meaning units based on the aims. The codes will be matched and grouped into

categories in accordance with similarities and dissimilarities. The categories will be scrutinised for underlying meanings, which will generate a number of sub-themes that reflect the content. The sub-themes will eventually be grouped under a few comprehensive themes.

Study three – validity and reliability test

Data collection

Eight patients with head and neck cancer from the Department of Maxillofacial and Oral Surgery (City of Jönköping), and eight healthy controls from the Public Dental Service Clinic (City of Jönköping) from study one will be recruited consecutively. The instruments described in study one will be completed at baseline. After 1-2 weeks, those patients (n=16) will complete the same instruments to evaluate test-retest reliability and validity.

Data analysis

Reliability

Homogeneity: Cronbach's alpha assesses internal consistency. According to Bland & Altman, Cronbach alphas of 0.70 to 0.80 are satisfactory for comparisons between groups, while an alpha of 0.90 is needed for clinical use.

Stability: Intraclass correlation coefficients (ICCs) with 95% confidence intervals are calculated per Shrout & Fleiss's ICC method based on a one-way analysis of variance (ANOVA). The concordance correlation coefficient (CCC) assesses reproducibility (temporal stability).

Validity

Content validity: Patients are asked, “Do you think the questions on aesthetics reflect the concerns you have with your mouth, your teeth and your tooth replacements (prostheses, crowns, bridges, and implants)?” They respond on a 0–10 VAS-scale with the anchors “very dissatisfied” and “very satisfied”.

Discriminative validity: Comparisons are made of OHIP-14 and GOHAI summary scores of each patient group with control groups and between patient groups. Relevant and statistically significant differences using t-tests and ANOVA are expected.

Convergent validity: Spearman rank order correlations (ρ), assess convergent validity between (i) OHIP summary scores and self-reported health and (ii) OHIP subscale scores and subscale scores of the SF-36 and EQ-5D.

Study four – Cost-effectiveness analysis

Background

In order for a method in health- and dental care to be considered cost-effective, it has to be a decent relation between its extra costs and effects (no exact threshold value exist in Sweden). A cost-effectiveness analysis estimates the incremental cost-effectiveness ratio (ICER) of a method in comparison with the best option (33). The outcome measure can be of any (relevant) kind, but usually it is recommended to use quality-adjusted life-years (QALYs) which also is preferred by the Swedish Dental and Pharmaceutical Benefits Agency (34). QALY combines preferences for health states (QALY-weight) with the number of years of that health state.

In order to capture the full consequences of a treatment, it is often necessary to model future costs and effects into a longer time horizon. Even though these models cannot be seen as evidence, they can provide the most accurate estimate on the long-term cost-

effectiveness and they can furthermore handle uncertainty in order to provide a decision-maker with relevant information (35).

Data collection

Costs and effects of different prosthodontic rehabilitations, fixed and removable dentures, will be compared with costs and effects of radiotherapy of patients with head and neck cancer. Data on resource use will be gathered in the intervention and translated into costs, representing their best alternative use. Productivity loss of patients unable to work will be estimated using the human capital approach. The main outcome measure in the analysis will be QALY. QALY-weights are derived indirectly from the instruments EQ-5D and SF-6D, and directly from the EQ-VAS, all of which are analysed in Study one in this project. Other outcome measures that are more directly derived from oral health related quality of life will be used too in order to examine their relevance.

Data analysis

A decision analytic model will be created that simulates the costs and effects of a long time horizon. In order to take into account the uncertainty in the parameter estimates derived from the intervention study, the model is run probabilistic. This means that the analysis is repeated 1,000 times, and each time the parameters are selected randomly from the distribution of the uncertainty surrounding the parameters. In this way, the total statistical uncertainty is illustrated. The results will be presented with and without including productivity losses.

Ethics

Ethical approval for the study was obtained from the Regional Ethical Committee (EPN) at Linköping University (2012/200-31; 2013/66-32).

Relevance of the project

The relevance of the project will be increased knowledge about the impact of replacement of extracted teeth with fixed dentures on oral health-related quality of life and general wellbeing, in patients with head and neck cancer after radiotherapy. Patients' recovery after disease in terms of wellbeing and oral health related quality of life may improve by fixed teeth. Professionals will benefit since this is an evaluation of the treatment outcomes. The society will also find the results important in order to evaluate the rehabilitation of patients that has received extensive oncological care. This may lead to overall reduced costs for medical and dental care.

Referenser

1. Hong WK. *Holland-Frei cancer medicine*. New York: McGraw-Hill Medical; 2010.
6. Jham BC, da Silva Freire AR. *Oral complications of radiotherapy in the head and neck*. *Braz J Otorhinolaryngol*. 2006 Sep-Oct;72(5):704-8.
8. Hedengran GHL. *Regulation of change in the dental regulation (1998:1338)*. In: Department S, editor.: *Swedish Parliament/Swedish Code of Statutes*; 2010.

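### Treatment is fixed by clinic, yet the between-group tests treat the 60 patients as independent; unless the intra-clinic correlation is very small or offset by the matching, type I error exceeds 5%

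*Protocol*

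**What the plan says.** Under Participants, the intervention arm has two sources. The first is given as "The intervention will include 30 patients with head and neck cancer recruited from a Department of Maxillofacial and Oral Surgery", namely Jönköping; the second is added as "and from the Department of Orofacial Medicine (the City of Stockholm, Stockholm County Council").

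For the control arm the protocol says: "Another 30 patients with the same disease will be matched controls recruited from another Department of Maxillofacial and Oral Surgery", namely Linköping. The remaining controls are described as coming "from five Departments of Orofacial Medicine (the Cities of Kalmar, Oskarshamn, and Västervik, Kalmar County Council; the Cities of Ljungby, and Växjö, Kronoberg County Council"). That is two intervention departments and six control departments, with none in common.

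The Data analysis section of Study one specifies "for comparison between two groups the Student t-test and the Mann-Whitney U-test". Adjustment is described only as follows: "in order to adjust for confounding variables such as age logistic regressions also are to be used". On the level it says: "The pre-chosen level of significance will be $p<0.05$ in all analyses". Neither clinic nor clustering is mentioned.

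**The concern.** Patients of one department share referral routes, oncology care, dental staff and local case mix, so their outcomes may resemble each other more than those of patients elsewhere. When the whole department is in one arm, this shared component does not cancel in the group difference. It adds to the variance of that difference, and a t-test or Mann-Whitney test on 30 against 30 patients does not see it. The nominal 5% then holds only if the intra-clinic correlation is zero or something offsets it.

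Three things are at stake.
- The p-values of every between-group result in Study one.
- The cost-effectiveness model in Study four. It draws its parameters from the uncertainty of the intervention data and claims to show the total statistical uncertainty. If the input distributions ignore clinic, it does not.
- The reader's view of precision. The protocol declines a power calculation, so the reported standard errors and p-values are the main guide to how much 60 patients can show.

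**Working it through.** In what follows, *r* is the intra-clinic correlation of the outcome. It is not the test-retest intraclass coefficient of Study three.

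**Inputs from the protocol.** 30 intervention patients in 2 departments; 30 controls in 6 other departments; unpaired two-group tests; level 0.05 (taken as two-sided, which the text does not state).

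**Assumptions, not in the protocol.** *r* from 0.01 to 0.10; patients per clinic; within-pair correlation ρ from 0 to 0.3. Two splits are used:
- equal: 15+15 against 6×5
- uneven: 25+5 against 20+2+2+2+2+2

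**Step 1: the plan's own figure.** With *r* = 0, simulated null trials of 30 against 30 reject in 5.0% (t-test) and 4.8% (Mann-Whitney). The nominal level is reproduced if the 60 patients are independent.

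**Step 2: variance inflation.** Per arm, design effect = 1 + *r*(Σm²/Σm − 1), where m is the number of patients in a clinic. With equal arms, the inflation V of the variance of the difference is the mean of the two.
- Equal: Σm²/Σm = 450/30 = 15 and 150/30 = 5. V = 1 + *r*(14 + 4)/2 = 1 + 9*r*.
- Uneven: 650/30 = 21.67 and 420/30 = 14. V = 1 + *r*(20.67 + 13)/2 = 1 + 16.83*r*.

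At *r* = 0.05 the arm design effects are 1.70 and 1.20 (equal), so V = 1.45 and the true standard error is √1.45 = 1.20 times the one used. For the uneven split they are 2.03 and 1.65, so V = 1.84 and the factor is 1.36.

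**Step 3: type I error without a matching offset.** Formula: 2(1 − Φ(1.96/√V)). The simulations used t-tests in null trials.

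| *r* | Equal: V | formula | simulated | Uneven: V | formula | simulated |
|---|---|---|---|---|---|---|
| 0.01 | 1.09 | 6.0% | 6.1% | 1.17 | 7.0% | 6.9% |
| 0.02 | 1.18 | 7.1% | 7.1% | 1.34 | 9.0% | 8.9% |
| 0.05 | 1.45 | 10.4% | 10.5% | 1.84 | 14.9% | 15.2% |
| 0.10 | 1.90 | 15.5% | 15.7% | 2.68 | 23.2% | 24.1% |

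For the equal split the Mann-Whitney test is close: 5.9%, 6.5%, 10.1% and 15.0%.

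**Step 4: offset from the matching.** If matching makes pairs correlated at ρ, the true variance falls while the unpaired test's standard error does not. The net factor is V − ρ, put into the same formula.

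| *r* | Equal, ρ = 0.2 | Equal, ρ = 0.3 | Uneven, ρ = 0.2 | Uneven, ρ = 0.3 |
|---|---|---|---|---|
| 0.01 | 3.8% | 2.7% | 4.6% | 3.5% |
| 0.02 | 4.8% | 3.7% | 6.6% | 5.4% |
| 0.05 | 8.0% | 6.8% | 12.6% | 11.4% |
| 0.10 | 13.3% | 12.1% | 21.4% | 20.4% |

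The two effects cancel when ρ = 9*r* (equal) or 16.83*r* (uneven). At *r* = 0.02 that is ρ = 0.18 or 0.34. At *r* = 0.05 it is 0.45 or 0.84.

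**The case against.** **The size is unknown, and even the direction is not certain.** A reader might infer that type I error definitely exceeds 5% and that the intervals are definitely too narrow. The documents do not support that. They give no intra-clinic correlation and no clinic sizes, and they call the controls matched while naming unpaired tests, which is conservative. At *r* of 0.01 to 0.02 the net error can be at or below 5%. The restriction to tumours up to T2 and the common exclusions narrow case mix, and self-completed questionnaires returned to one coordinator leave little room for a rater effect by clinic. All of this stands and makes the finding conditional. It does not remove it: at *r* = 0.05 or above the error stays over 5% at every pair correlation tried.

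**The analysis section is a general list, and a statistical analysis plan may add to it.** The list of confounders is open, and no confidence intervals are specified for the Study one group comparisons. That is fair. But the two-group tests are named, and they do not fit the recruitment scheme in the same document. This is a stated choice that fits badly, not a detail left for later.

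**No model repairs this well.** A random clinic intercept with a clinic-type term was simulated under these clinic sizes. The clinic variance was estimated as zero in 45% to 52% of trials at *r* = 0.05. With 5 degrees of freedom, the error fell to about 1-2% at *r* of 0.01 to 0.02. Each arm has only one maxillofacial department, so a clinic-type term rests on two clinics. This stands, and such a model should not be the main analysis.

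**Bias matters more than precision.** Agreed: systematic clinic differences are confounded with treatment. The two problems are separate, though. Random clinic variation can be shown in the interval even where the bias cannot be removed.

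**Conclusion.** The mismatch is certain: arm is fixed by clinic, two departments against six others, and the named tests assume independent patients. Its consequence is conditional. Unless the intra-clinic correlation is very small (about 0.01-0.02) or the matching offsets it, type I error exceeds 5% and the standard error is understated, by a factor of 1.20 to 1.36 at a correlation of 0.05.

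The error range, from 6% to 24% without a matching offset, rests on assumed correlations and assumed clinic sizes. The lower figures with an offset rest on an assumed pair correlation. Nothing in the protocol shows where in this range the trial lies, which is why a sensitivity range is more defensible than a single correction.

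A reader might also infer that a clinic-adjusted model would isolate the effect of fixed dentures. It would not. No department contributes to both arms, so systematic differences between departments remain part of the contrast whatever the analysis.

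**What to change.** In the Data analysis section of Study one:

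1. Report each main group difference, adjusted for its baseline value, with a confidence interval.
2. Beside it, give a sensitivity interval with the standard error multiplied by the square root of the design effect. Compute the design effect from the clinic sizes actually recruited, over a stated range of assumed intra-clinic correlations, for example 0.01 to 0.10.
3. If wanted, show a random clinic intercept with small-sample degrees of freedom as supportive only, because eight clinics estimate the clinic variance poorly.
4. State that the contrast compares clinics' whole care, that systematic clinic differences stay confounded with dentures, and that no analysis of these data removes them.

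In the Data analysis section of Study four, base the parameter distributions on the wider uncertainty, or run the model under both sets.

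No new patients or measurements are needed. The cost is wider intervals (1.20 to 1.36 times as wide at a correlation of 0.05 under the two splits above) and a more limited conclusion.

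### Controls are called matched, but the matching is undefined and no between-group analysis named in the protocol uses it, which costs precision if the matching factors predict outcome

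*Protocol*

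**What the plan says.** On the design, Methods, Participants states "The intervention will include 30 patients with head and neck cancer", and then "Another 30 patients with the same disease will be matched controls recruited from another Department of Maxillofacial and Oral Surgery". The exclusion criteria mention the matching once more: "patients in the matched control group financing fixed oral prosthesis themselves". Neither place gives matching variables, a matching ratio or a way of forming pairs. Background data such as sex, age, diagnosis and TNM class are to be collected, but none is named as a matching factor.

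On the analysis, Study one, Data analysis gives:

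- Two groups: "for comparison between two groups the Student t-test and the Mann-Whitney U-test".
- Three or more groups: two-way analysis of variance and Kruskal-Wallis.
- Proportions: "For comparison of proportions between groups the Chi-square-test including standardized residual are to be used".
- Within patients: "For analysing changes over time the paired t-test or the Wilcoxon Signed Rank Test", with McNemar for dichotomised variables.
- Regression: multiple and logistic regression for prediction, and "in order to adjust for confounding variables such as age logistic regressions also are to be used".

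On sample size, Design and setting says that a power calculation is not relevant, "due to the restricted eligible/consecutive sample as well as the restricted time schedule".

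**The concern.** Matching on factors that predict outcome makes the two groups more alike than two unrelated samples would be. The true sampling variance of the group difference is then smaller than an independent-samples formula assumes. The gain is realised only if the analysis contains the matching, either as a pair effect or through the matching factors as covariates. None of the between-group methods named here does so.

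The stated adjustment does not fill the gap. It is logistic regression, while SF-36v2, OHIP-14, GOHAI, JFLS-8 and OAS mainly yield scores. Multiple regression is listed, but for prediction, and the matching factors are not mentioned with it.

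What is at stake is precision. The sponsor says the sample and the time schedule are restricted, so the analysis is one of the few places where precision can still be gained.

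**Working it through.** **Inputs from the protocol.** 30 intervention patients and 30 controls (Participants); significance level 0.05 (Study one, Data analysis). The protocol states no power, effect size, standard deviation or within-pair correlation, so there is no figure of the plan's own to reproduce.

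**Assumptions.** Two-sided testing (sidedness is not stated), normal outcomes with SD 1, a true difference of d = 0.6 SD, and a within-pair correlation r from 0 to 0.5. The values of d and r are illustrative.

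**Formulas, individual pairs, n = 30 per group.**

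- Standard error used by the independent t-test: sqrt(2/n) = sqrt(2/30) = 0.258.
- True standard error: sqrt(2(1 − r)/n).
- Ratio of the first to the second: 1/sqrt(1 − r).
- Actual type I error of the independent test (normal approximation): 2 × [1 − Φ(1.96/sqrt(1 − r))].

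Example, r = 0.3: true standard error = sqrt(2 × 0.7/30) = 0.216; ratio = 0.258/0.216 = 1.195, so about 20% too large; type I error = 2 × [1 − Φ(2.34)] = 0.019.

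Power was found by simulating both t-tests (100,000 trials per setting):

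| Assumed r | Standard error too large by | Actual type I error, independent test | Power at 0.6 SD, independent | Power at 0.6 SD, paired |
|---|---|---|---|---|
| 0 | 0% | 5.0% | 63% | 61% |
| 0.1 | 5% | 3.9% | 63% | 66% |
| 0.2 | 12% | 2.8% | 64% | 71% |
| 0.3 | 20% | 1.9% | 65% | 77% |
| 0.5 | 41% | 0.6% | 67% | 89% |

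The pattern is the same at 0.5 SD: about 47% to 48% power with the independent test throughout, against 47%, 50%, 55%, 61% and 75% paired.

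**Group matching.** Here there are no pairs, so the check used three strata with 10 patients per group in each. The unadjusted t-test was compared with a linear model containing group and stratum, again at d = 0.6 SD:

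| Assumed share of variance explained by strata | Type I error, unadjusted | Power, unadjusted | Power, adjusted |
|---|---|---|---|
| 0 | 5% | 63% | 63% |
| 10% | 3.9% | 63% | 67% |
| 20% | 2.7% | 64% | 72% |
| 30% | 1.9% | 65% | 78% |

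Under either form of matching, the unadjusted test leaves the variance due to the matching factors in its error term.

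**The case against.** The case against is substantial, and parts of it stand.

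- **Pairs are not stated.** A reader might infer 1:1 pairing from 30 and 30. The protocol does not say so, and equal totals fit group matching just as well. A paired test would not then apply, and independent-group methods adjusted for the matching factors would be suitable. This stands as a limit on the remedy. It does not remove the point, because the named tests are unadjusted and lose precision under group matching too.
- **The listed regressions could carry the matching factors.** That is true, so it would be too strong to say the matching is thrown away. But multiple regression is assigned to prediction, only logistic regression is assigned to adjustment, and neither is tied to the matching.
- **The loss may be negligible.** This stands. The two groups come from different clinics, so matched patients share no site, which removes one source of correlation. At zero correlation the independent test is exactly right and strict pairing is slightly worse.
- **A statistical analysis plan may settle this.** It might. However, the protocol does not leave the between-group tests open: it names them, and they do not use the matching it declares.

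A reader might also infer that ordinary logistic regression is biased because the study is labelled case-control. The documents do not support this. Groups are defined by treatment and outcomes are measured afterwards, so controls are matched to treated patients and not to outcome cases. The bias that comes from sampling matched on outcome does not arise.

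**Conclusion.** The point holds in a limited form. The protocol declares matched controls, does not define the matching, and names no between-group analysis that uses it. Followed as written, the tests are valid but conservative whenever the matching factors predict outcome.

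The size depends wholly on a correlation the document does not give. For an assumed 0.6 SD effect the paired analysis gains about 3 points of power at r = 0.1, 7 at 0.2, 12 at 0.3 and 22 at 0.5, and loses 1 to 2 points at r = 0.

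A reader might conclude that the planned intervals and p-values are simply wrong, or that false positives are inflated. Neither follows. With zero correlation the intervals are correct, and with positive correlation they are too wide, with type I error below 5%. Only a negative within-pair correlation would inflate it (about 7.4% at r = −0.2), and matching is not expected to produce that.

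**What to change.** 1. **Participants.** State the matching variables and whether matching is individual or by group. Record the pair or stratum number at recruitment, since it may not be recoverable later.
2. **Study one, Data analysis, continuous scores.** Make the main between-group comparison a linear model with group and the matching factors. The factors should be among the background data already collected, or be added to them. If individual pairs are formed, use a mixed model with pair as a random effect; it keeps patients left without a partner, which matters in a restricted consecutive sample.
3. **Study one, Data analysis, binary items.** Use logistic regression with group and the matching factors or, if paired, McNemar's test or conditional logistic regression.

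The cost is a few sentences, one stored number per patient and a little more analysis work. If the within-pair correlation turns out to be zero, a strictly paired analysis loses about 1 to 2 points of power; in the stratum example above, the adjusted linear model loses almost nothing.
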